### **8.2.10. Total Duration of ICU Stay from Baseline through Day 28**

Duration of ICU stay through 28 days post-baseline will be summarized by treatment arm. Duration will be measured in days.

The duration of ICU stay will be compared between treatment groups using the Wilcoxon Rank Sum Test.

If fewer than five patients report ICU stay, this outcome will be reported descriptively.

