## Document History

Version	Description
2.0	
Added estimand statement, aligned with Protocol v3.0, specified how mortality factors into the primary analysis, and added baseline neurotoxicity as a pre-specified covariate.

3.0	

- Added use of a fixed-sequence approach and specification of key (alpha-protected) secondary efficacy endpoints with details regarding analysis

- Changed analyses of hospital durations from ANCOVA to Wilcoxon rank sum test.

- Added clarification and details regarding handling of missing data; including the addition of multiple imputation used in primary and key secondary analyses.

- Added additional subgroup analyses of the primary and key secondary outcomes, including analyses by country (United States, India), and by timing of bite or symptom onset to receipt of study drug (<5 hours, <math>\geq 5</math> hours)

- Added SAS code for primary and key secondary endpoints.

- Added clarification on the analysis of mortality regarding what will be done in the event of too few deaths for formal statistical models.

- Fixing various typos from the prior version.

4.0	

- Specified the use of FDA Medical Queries (FMQs) for safety endpoints.

- Added SAS code for multiple imputation.

- Specified sensitivity analysis for handling missing data.

- Defined method for ensuring that SSS-AUC Day 7 uses 168 hours as duration of elapsed time for all patients.

- Added country as a covariate for the analysis of the primary and key secondary efficacy endpoints.

- Added a new key secondary endpoint: Numeric Pain Rating Score area under the curve from Baseline to Day 3.

- Revised the analysis of one of the secondary outcomes: coagulation laboratory values.

- Added graphical presentations for subscores of the Snakebite Severity Score.

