### **3.5. Method of Assigning Subjects to Treatment Groups**

In this parallel-group randomized study, subjects who meet study entry criteria will be randomly assigned in a 1:1 ratio to varespladib-methyl or placebo. The randomization schedule, which will be computer generated using a permuted block algorithm, will randomly allocate IP to randomization numbers. The randomization numbers will be assigned sequentially through a central interactive web response system (IWRS) as subjects are entered into the study. The randomization schedule will be stratified by age group (5 to  $< 11$  years, 11 to  $< 18$  years, and  $\geq 18$  years) and by the presence or absence of moderate to severe neurotoxicity (SSS nervous system subscore of 0–1 or  $\geq 2$ ) at Baseline, resulting in 6 strata in total. Study center will not be a blocking factor in the randomization schedule. The block sizes will not be divulged to the Sponsor or the investigative team. No one involved in the study performance will have access to the randomization schedule before official unblinding of treatment assignment. The

randomization schedule will be prepared by the clinical research organization (CRO) before the start of the study. No subject will be randomized into this study more than once.

A subject will be considered randomized when the IWRS has given the treatment number to be allocated.

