## 8.2. Other Secondary Efficacy Analyses

The other secondary efficacy analyses will be interpreted as exploratory analyses. All secondary endpoints will be analyzed according to the prespecified assessment timepoints listed in the protocol. Statistical models will include covariates for baseline SSS, baseline neurotoxicity (Yes, No; based on the SSS neurological system subscore), age group (5-17, 18+), and, when available, the baseline value of the particular endpoint unless otherwise specified below. A sensitivity analysis will include as a covariate yes/no completion of an initial dose of antivenom prior to randomization. The methods described here are what is currently planned. However, for each analysis, we will examine the distribution of the strata pooled over treatment and placebo. If the data are unlikely to support the planned analysis or if the model fails to converge, removal of covariates and different estimation routines will be attempted and described in the CSR.

### 8.2.1. Complete SSS from Baseline through Day 7

The complete SSS (all sub-sections including pulmonary, cardiovascular, hematologic, renal, nervous system, gastrointestinal, and local wound) from baseline through Day 7 after first dose will be summarized using descriptive statistics of observed values and changes from baseline.

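### ICU stay (SAP 8.2.10) is compared with an unstratified Wilcoxon test although randomisation is stratified: the test is valid, but it loses power to the extent that neurotoxicity and age predict ICU stay

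*SAP*

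**What the plan says.** SAP 8.2.10 states: "The duration of ICU stay will be compared between treatment groups using the Wilcoxon Rank Sum Test". It adds one fallback: "If fewer than five patients report ICU stay, this outcome will be reported descriptively". It does not say whether patients never admitted to ICU enter the test as 0 or are left out. SAP 6.1.7.10 sums the ICU episodes and does not settle this either.

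SAP 3.5 stratifies the randomisation by three age groups and by a nervous system subscore of 0-1 or at least 2, "at Baseline, resulting in 6 strata in total". Country is not among the strata, and "Study center will not be a blocking factor in the randomization schedule".

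SAP 8.2 gives default covariates for the statistical models of the other secondary endpoints: baseline SSS, neurotoxicity, two-level age group and, where available, the baseline value of the endpoint. The default applies unless the endpoint's own section says otherwise. The same section sets the status of these endpoints: "The other secondary efficacy analyses will be interpreted as exploratory analyses".

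Planned Table 14.2.12.1 holds the overall Wilcoxon results. Tables 14.2.12.2, 14.2.12.3 and 14.2.12.5 repeat the test by age group, neurotoxicity and country. Those are separate subgroup tests, not one pooled stratified test.

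**The concern.** Stratified allocation keeps neurotoxicity and age balanced between the arms. The plain Wilcoxon statistic is nevertheless judged against a null variance that includes the spread between strata, which the design has largely removed from the treatment comparison. If neurotoxic patients go to ICU more often or stay longer, that variance is too large for this design, and a true reduction in ICU stay is more likely to be missed.

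Elsewhere the plan uses these factors. The primary ANCOVA does (SAP 8.1.1), and so does the ANCOVA for US hospital stay (SAP 8.2.11). Skewed durations are a good reason to work on ranks, but not a reason to leave out the stratification factors: SAP 8.1.1 already plans a covariate-adjusted rank regression as a sensitivity analysis. At stake is the efficiency of one secondary comparison, not the type I error of the trial.

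**Working it through.** **1. The plan's own figure.** The only power statement concerns the primary endpoint (SAP 3.2): difference 1.1, SD 1.75, two-sided 0.05, power 85%. The normal approximation gives n per arm = 2(1.960 + 1.036)² × 1.75² / 1.1² = 2 × 8.98 × 3.0625 / 1.21 = 45.5, so 46. The t-based calculation gives 46.4, so 47 per arm and 94 in total, with power 85.4%. Allowing for 15% withdrawal, 94 / 0.85 = 110.6, against about 110 planned. The figure reproduces, but it says nothing about ICU stay.

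**2. Mechanism.** With m of N patients treated, the Wilcoxon null variance is V = m(N − m)/(N − 1) × (variance of the ranks). If the strata explain a share R² of the rank variance and allocation is balanced within strata, the true variance is roughly (1 − R²)V. The true size is then about 2Φ(−1.96/√(1 − R²)). Illustrative values:
- R² = 0: 5.0%
- R² = 0.10: 1.96/0.949 = 2.07, size 3.9%
- R² = 0.35: 1.96/0.806 = 2.43, size 1.5%

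The size cannot exceed 5% by this route.

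**3. Simulation.** From the documents: 110 patients, 1:1 allocation, six strata, two-sided 5%. Assumed, because the documents give nothing:
- blocks of 4; 20% children
- ICU stay 0 if none, otherwise log-normal with median 2 days and log-SD 0.8
- longer stays in neurotoxic patients: factor 1.5 where their ICU rate is 60%, factor 2 where it is 80-90%
- under the alternative, ICU odds ratio 0.3 and duration ratio 0.7

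Age is a stratum in these runs but has no prognostic effect. Each setting has 6,000 trials, so the standard error of a 5% size is √(0.05 × 0.95/6000) = 0.3 points. W is the plain Wilcoxon test, VE6 a van Elteren test on all six strata, and RR a rank analysis adjusted for neurotoxicity and two-level age.

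| Neurotoxic share | ICU rate, subscore 0-1 / ≥2 | Size % W / VE6 / RR | Power % W / VE6 / RR | RR − W |
|---|---|---|---|---|
| 20% | 30 / 30 | 4.9 / 4.7 / 4.8 | 72.7 / 71.8 / 72.8 | 0 |
| 5% | 20 / 60 | 4.7 / 5.1 / 5.1 | 56.0 / 56.3 / 57.9 | 2 |
| 10% | 20 / 60 | 4.5 / 5.3 / 5.4 | 58.3 / 59.9 / 61.4 | 3 |
| 20% | 20 / 60 | 3.5 / 4.8 / 4.7 | 62.2 / 66.0 / 66.7 | 4 |
| 5% | 20 / 90 | 3.8 / 4.9 / 5.3 | 47.3 / 54.6 / 55.8 | 9 |
| 10% | 20 / 90 | 2.4 / 5.1 / 4.5 | 42.5 / 57.5 / 58.7 | 16 |
| 20% | 20 / 80 | 2.0 / 5.0 / 5.1 | 50.9 / 65.6 / 66.0 | 15 |
| 30% | 20 / 80 | 1.5 / 5.4 / 4.9 | 53.8 / 70.5 / 71.2 | 17 |

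A separate set of runs, with van Elteren stratified by neurotoxicity only or a rank analysis, gave gains of about 0, 2-5 and 15-16 points for non-prognostic, moderate and strong strata.

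**4. ICU patients only.** Here the comparison is restricted to admitted patients, with duration ratio 0.5 and no effect on admission:

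| Neurotoxic share | ICU rate, subscore 0-1 / ≥2 | Size % W | Power % W / VE6 / RR |
|---|---|---|---|
| 10% | 20 / 60 | 4.8 | 51.4 / 45.0 / 50.7 |
| 20% | 20 / 60 | 5.0 | 57.6 / 52.4 / 57.7 |
| 30% | 20 / 80 | 4.1 | 68.3 / 68.6 / 72.8 |

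The conservatism largely disappears. Six sparse strata cost 5 to 6 points in the first two settings, while the rank regression loses less than 1. With non-prognostic strata, the separate runs put the loss from neurotoxicity-only stratification or rank regression at about 2 points at most.

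**The case against.** The strongest reply is that the plan contains no error. A test with size at or below 5% is valid, and the sponsor chose it deliberately. The Document History for version 3.0 records: "Changed analyses of hospital durations from ANCOVA to Wilcoxon rank sum test". That stands.

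A reader might infer that SAP 8.2.10 contradicts the default covariates of SAP 8.2. The documents do not support this: the default is for statistical models and yields to endpoint-specific text, and SAP 8.2.10 is such text.

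A reader might also take the pooling of the two countries as part of the same defect, since SAP 8.2.11 expects hospital stays to differ by country. Country is not a randomisation stratum, so adjusting for it is ordinary covariate adjustment. Any gain from it should not be credited to the mechanism described here.

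The size of the loss is also open. SAP 8.2.2 reports unexpectedly few severely neurotoxic patients, which bears only indirectly on the cut at 2, and SAP 6.1.2 anticipates few children. Both tend to shrink the loss. They do not remove it if the factor is strong: a 5% neurotoxic group with ICU rates of 20% and 90% still costs 9 points. The subgroup tables will show differences between strata, but they do not supply a pooled stratified test.

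**Conclusion.** The point holds as a conditional loss of efficiency on an exploratory endpoint outside the fixed testing sequence. The plain Wilcoxon test is valid. At 110 patients, with patients without ICU stay entered as 0, it gives up about 0 power points if the strata are not prognostic and 2 to 5 if they are moderately prognostic. The loss is around 16 (15 to 17) if they are strongly prognostic and the neurotoxic group is at least a tenth of the trial.

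These figures rest on assumed ICU rates, durations and treatment effects. Only neurotoxicity was made prognostic, so the contribution of age was not measured.

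Two stronger readings are tempting and not supported: that the test is wrong, and that it is too conservative whatever the data look like. The first fails because the size never exceeds the nominal level beyond simulation error. The second fails because the loss vanishes when the strata do not predict ICU stay, and largely does so if only ICU patients are compared. Nor is the remedy wholly free.

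**What to change.** In SAP 8.2.10 and the ICU rows of Table 14.2.12.1, before unblinding:

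- Make the comparison a rank regression, as in the sensitivity analysis of SAP 8.1.1, with treatment, baseline neurotoxicity (0-1 or at least 2) and age group (5-17 or 18+). Baseline SSS and country may be added as ordinary covariates.
- Alternatively, use a van Elteren test on collapsed strata (neurotoxicity), not on all six cells.
- State that patients with no ICU stay enter as 0. This keeps all randomised patients in the comparison and avoids selecting on admission, which treatment may change.
- Keep the plain Wilcoxon test as supportive, and keep the existing rule for fewer than five ICU patients.

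The cost is a sentence or two of SAP text and a few lines of code. The statistical price is about 1 to 2 power points if the strata turn out not to be prognostic. It would be higher, 5 to 6 points in the runs above, if all six sparse strata were used in ICU patients only.

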### **8.2.11. Total Duration of Hospitalization from Baseline through Day 28**

Duration of hospitalization through 28 days post-baseline will be summarized by treatment arm separately for the United States and India, recognizing the anticipated differences in the typical duration of hospital stay for patients experience snakebite envenoming in the two countries. Duration will be measured in days.

For patients enrolled in the United States, the duration of hospitalization will be compared between treatment groups using ANCOVA with baseline SSS, age group, and baseline neurotoxicity as covariates.

For patients enrolled in India, the duration of hospitalization will be compared using the Wilcoxon Rank Sum Test. A non-parametric test will be used for the data from India because the data are anticipated to exhibit rightward skew, with a few patients having a much longer duration of hospitalization than most.

Only hospitalization stays from baseline through Day 28 will be included in this analysis.

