#### **3.2. Sample Size and Power**

The sample size for this phase 2 study was determined by a formal power calculation based on the primary efficacy endpoint. This study was powered at 85% to detect a statistically significant (2-sided alpha = 0.05) treatment effect. The assumptions are the following:

- 2-sided alpha level 5%
- Power 85%
- Randomization ratio 1:1
- A minimum difference in the change from Baseline to the average at 6- and 9-hour pulmonary, cardiovascular, hematologic, renal, and nervous system subscores of the SSS of 1.1 points and a standard deviation 1.75

A sample size of 94 patients will provide 85% power to identify a difference of 1.1 in the primary outcome (two-sided alpha = 0.05). The sample size has been calculated using nQuery 8.

The randomization scheme will be 1:1 stratified by age group (5 to < 11, 11 to < 18, and  $\geq$  18 years old) and by the presence or absence of neurotoxicity (SSS nervous system subscore of 0–1 or  $\geq$  2) at Baseline, resulting in 6 strata in total.

Because we anticipate up to 15% withdrawal through the end of the study, we requested permission to enroll up to 110 patients to ensure adequate power for secondary outcomes.

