## **4. Statistical Analysis and Reporting**

### **4.1. Introduction**

Data processing, tabulation of descriptive statistics, calculation of inferential statistics, and graphical representations will primarily use SAS (release 9.4 or higher). If the use of other software is warranted, the final statistical methodology report will detail what software was used for what purposes.

Continuous (quantitative) variable summaries will include the number of subjects (n) with non-missing values, mean, standard deviation, median, 25th percentile, 75th percentile, minimum, and maximum.

Categorical (qualitative) variable summaries will include the frequency and percentage of

subjects who are in the particular category or each possible value. In general, the denominator for the percentage calculation will be based upon the total number of subjects in the study population for the treatment groups, unless otherwise specified.

The minimum and maximum will be reported with the same degree of precision (i.e., the same number of decimal places) as the observed data. Means will be reported to 1 degree of precision more than the observed data and measures of spread will be reported to 2 degrees of precision more than the observed data. Medians will be reported to the degree of precision measured.

Percentages will be presented to 1 decimal place, unless otherwise specified.

Unless otherwise indicated, all statistical tests will be conducted at the 0.05 significance level using 2-tailed tests, and *P* values will be reported. Corresponding 95% confidence intervals (CIs) will be presented for statistical tests.

This study is considered a confirmatory study. Statistical tests will be regarded as formal tests of specific hypotheses.

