#### **6.1.7.10. Duration of ICU Stay**

The length of ICU stay from baseline to Day 28 will be calculated using the following duration in hours

$$\sum_{\text{for each episode}} (\text{ICU discharge date and time} - \text{ICU admission date and time})$$

The duration of ICU stay will be truncated at Day 28. If a discharge date and time is after Day 28, it will be replaced by Day 28.

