#### **6.1.7.11. Duration of hospitalization**

The length of hospital stay from baseline to Day 28 will be calculated using the following duration in hours

$$\sum_{\text{for each admission}} (\text{discharge date and time} - \text{admission date and time})$$

The duration of hospitalization will be truncated at Day 28. If a discharge date and time is after Day 28, it will be replaced by Day 28.

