Table 14.2.11.1 Summary of Head Lift Duration through Day 7 ITT Population
Table 14.2.11.2 Statistical Analysis of Head Lift Duration through Day 7 in Subjects with SSS Nervous System Subscore $\geq 2$ at Baseline: Logistic MMRM ITT Population
Table 14.2.12.1 Statistical Analysis of Ventilatory Support, ICU Stay, and Hospitalization Durations through Day 28: Wilcoxon Rank Sum Test ITT Population
Table 14.2.12.2 Statistical Analysis of Ventilatory Support, ICU Stay, and Hospitalization Durations through Day 28: Wilcoxon Rank Sum Test by Age Group ITT Population
Table 14.2.12.3 Statistical Analysis of Ventilatory Support, ICU Stay, and Hospitalization Durations through Day 28: Wilcoxon Rank Sum Test by Neurotoxicity Status ITT Population
Table 14.2.12.4 Statistical Analysis of Ventilatory Support, ICU Stay, and Hospitalization Durations through Day 28: Wilcoxon Rank Sum Test by Antivenom Prior to Baseline ITT Population
Table 14.2.12.5 Statistical Analysis of Ventilatory Support, ICU Stay, and Hospitalization Durations through Day 28: Wilcoxon Rank Sum Test by Country ITT Population
Table 14.2.13 Statistical Analysis of All-cause Mortality through Day 28: Kaplan-Meier and Cox Model Results ITT Population
Table 14.2.14.1 Statistical Analysis of PGIC from Baseline through Day 7: MMRM ITT Population
Table 14.2.14.2 Statistical Analysis of PGIC from Baseline through Day 7: MMRM by Age Group ITT Population
Table 14.2.14.3 Statistical Analysis of PGIC from Baseline through Day 7: MMRM by Neurotoxicity Status ITT Population
Table 14.2.14.4 Statistical Analysis of PGIC from Baseline through Day 7: MMRM by Antivenom Status ITT Population
Table 14.2.15.1 Statistical Analysis of PSFS from Baseline through Day 28: MMRM ITT Population
Table 14.2.16.1 Statistical Analysis of CGI-I from Baseline through Day 7: MMRM ITT Population
Table 14.2.16.2 Statistical Analysis of CGI-I from Baseline through Day 7: MMRM by Age Group ITT Population
Table 14.2.16.3 Statistical Analysis of CGI-I from Baseline through Day 7: MMRM by Neurotoxicity Status ITT Population
Table 14.2.17 Exploratory Analysis of SSS Scores through Day 28 ITT Population
Table 14.2.18 Exploratory Analysis of Compressed SSS Scores through Day 28 ITT Population
Table 14.2.19 Exploratory Analysis of Grip Strength through Day 28PE ITT Population
Table 14.2.20 Exploratory Analysis of SSS Neurologic System Subscore through Day 7 ITT Population

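### The SAP gives contradictory tests for duration of hospitalization, and its stay formulas start the clock at admission rather than at baseline

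*SAP*

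**What the plan says.** Protocol section 6 lists total hospitalization time through Day 28 as a secondary endpoint, without a country split. SAP 8.2.11 summarises it separately for the two countries because typical stays are expected to differ. For the U.S.: "For patients enrolled in the United States, the duration of hospitalization will be compared between treatment groups using ANCOVA", adjusted for baseline SSS, age group and baseline neurotoxicity. For India: "For patients enrolled in India, the duration of hospitalization will be compared using the Wilcoxon Rank Sum Test", because right skew is expected there. No test across both countries is named.

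The table list in SAP 13.2 reads differently: "Table 14.2.12.1 Statistical Analysis of Ventilatory Support, ICU Stay, and Hospitalization Durations through Day 28: Wilcoxon Rank Sum Test ITT Population". That title has no country split. Table 14.2.12.5 is a Wilcoxon analysis by country, so it covers the U.S. as well. No listed table of hospital stay uses ANCOVA.

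On derivation, SAP 6.1.7.11 says: "The length of hospital stay from baseline to Day 28 will be calculated using the following duration in hours". The formula is the sum over admissions of discharge minus admission, and the only truncation is at Day 28. SAP 6.1.7.10 does the same for ICU stay: "The length of ICU stay from baseline to Day 28 will be calculated using the following duration in hours". SAP 8.2.10 and 8.2.11 report both durations in days. Section 8.2.11 adds: "Only hospitalization stays from baseline through Day 28 will be included in this analysis".

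SAP 8.2 treats these other secondary analyses as exploratory.

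**The concern.** A programmer following 8.2.11 and one following the table list would produce different results for the same endpoint. Under 8.2.11 there are two p-values from two methods and no answer for the trial as a whole. Under Table 14.2.12.1 there is one p-value, from a test that pools countries whose stays the SAP itself expects to differ; the between-country spread then obscures the treatment comparison. Leaving the choice open until results are visible is what a prespecified plan should prevent.

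Separately, the stay as computed is not the stay as named. Hours between admission and baseline precede randomization and cannot reflect treatment, yet the formula includes them. The absolute durations matter beyond the test because SAP 11.2 uses hospital stay in the pharmacoeconomic analysis.

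**Working it through.** **1. The plan's own power figure.** SAP 3.2 says: "A sample size of 94 patients will provide 85% power to identify a difference of 1.1 in the primary outcome". With difference 1.1, SD 1.75 and two-sided alpha 0.05, the normal approximation gives n per arm = 2 × [1.75 × (1.960 + 1.036) / 1.1]² = 45.4, rounded up to 46, or 92 in total. The noncentral t gives 47 per arm, or 94, with power 85.4%. The stated figure reproduces, but it concerns the primary endpoint only. No power is stated for hospital stay.

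**2. The sources side by side.**

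| Source | U.S. | India | Overall |
|---|---|---|---|
| SAP 8.2.11 | ANCOVA | Wilcoxon | none named |
| Table 14.2.12.1 | – | – | Wilcoxon, unstratified |
| Table 14.2.12.5 | Wilcoxon | Wilcoxon | – |

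The conflict covers both the U.S. method and whether an overall test exists.

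**3. Illustrative power.** Nothing in the documents fixes the effect, SD or country split, so these inputs are assumptions: log-normal stay, log-SD 0.8 in both countries, placebo medians 1.5 days (U.S.) and 4 days (India), the same treatment ratio in both countries, and 54 per arm. The U.S. test is simulated as a t-test on days without covariates, India as a Wilcoxon test. The stratified (van Elteren) statistic is Σ wₖ[Rₖ − nₖ(Nₖ + 1)/2] with wₖ = 1/(Nₖ + 1), divided by the square root of Σ wₖ² nₖmₖ(Nₖ + 1)/12. Here Rₖ is the active-arm rank sum in country k, nₖ and mₖ are the arm sizes, and Nₖ = nₖ + mₖ. Per SAP 4.1, "all statistical tests will be conducted at the 0.05 significance level using 2-tailed tests".

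| | Ratio 0.7 | Ratio 0.6 |
|---|---|---|
| U.S. alone, 27 per arm | 29% | 52% |
| India alone, 27 per arm | 34% | 61% |
| Single country, splits 14/40 to 40/14 per arm | 16–49% | 29–78% |
| Unstratified Wilcoxon, same splits | 47–51% | 81–83% |
| Stratified by country, same splits | about 61% | 88–89% |

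Simulation error is about one percentage point. With no treatment effect, the unstratified test rejects in about 2% of trials against a nominal 5%: it is valid but wasteful. In the equal split, the two country tests disagreed on significance in 43% (ratio 0.7) to 49% (ratio 0.6) of trials, although the same ratio held in both countries.

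**4. The start of the clock.** The stated formula is Σ(discharge − admission), with discharge capped at Day 28. A stay measured from baseline is Σ[min(discharge, Day 28) − max(admission, baseline)]. For the index admission the two differ by baseline minus admission, which the documents do not quantify. To gauge its statistical effect, assume a gap uniform over 0–4 h or 0–10 h and a stay SD of 24–72 h. The mean rises by 2 h or 5 h. The largest SD inflation is √[1 + (10²/12)/24²] = 1.007, under 1%. The gap closes before randomization, so its distribution is the same in expectation in both arms.

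**The case against.** The country-specific analysis is deliberate, and 8.2.11 gives its reason. SAP 8.2 calls the endpoint exploratory, and it lies outside the fixed testing sequence, so no confirmatory claim depends on it. Choosing a stratified test as the main one is partly a matter of judgement. The word baseline in 6.1.7.10, 6.1.7.11 and 8.2.11 makes the intent clear, and Protocol 7.2 describes screening, enrolment and first treatment in one visit at admission, so the gap should often be short.

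Much of this stands, and it limits the weight of the point. It does not reconcile 8.2.11 with the table list. SAP 13 calls the table numbers placeholders, but not the methods in the titles. Nor does clear intent repair a formula that computes something else. Category 2 patients (Protocol 8.2.1) have completed an initial antivenom dose before eligibility, so for them some treatment time precedes baseline.

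A reader might go further on the clock, and the documents do not support these readings:
- The 10-hour entry limit is not the size of the pre-baseline time. It runs from symptom onset to eligibility assessment, not from admission to baseline.
- Pre-baseline hours do not bias the arm difference or materially cost power (step 4).
- The sentence limiting the analysis to stays from baseline need not drop the index admission. That reading would leave almost no data. It needs clarifying, no more.

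**Conclusion.** The contradiction between SAP 8.2.11 and Tables 14.2.12.1 and 14.2.12.5 is established from the text. So are the missing start rule in 6.1.7.10 and 6.1.7.11 and the conflict between hours and days.

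A reader might infer that the SAP has no overall test of hospital stay. That is true of 8.2.11 only; Table 14.2.12.1 is one, but it ignores country.

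A reader might also infer that splitting by country halves the power. The documents cannot support a single figure. In general, a test with 85% power on the full sample has Φ(2.996/√2 − 1.960) = 56% on half of it, a relative loss of about one third. In the simulation, the equal-split loss against the stratified test is close to half at ratio 0.7 (29% and 34% against 61%) and smaller at ratio 0.6 (52% and 61% against 89%). It also varies with the country split. All of this rests on the assumed distribution, effect and split, and on a U.S. test without the ANCOVA covariates.

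The supportable statement is that, under those assumptions, the stratified test beats either country test and gains roughly 5 to 14 points over the unstratified one (61% against 47–51%; 88–89% against 81–83%). The point is worth correcting but affects an exploratory endpoint. The pre-baseline hours are a definition error, not a source of bias.

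**What to change.** - In 8.2.11, make the overall comparison one Wilcoxon test stratified by country (van Elteren) in the ITT population.
- Keep the country-specific results as supportive, with one stated method for both countries. Report medians by arm within each country: a common ratio does not give a common shift in days (at ratio 0.7 the assumed medians fall by 0.45 and 1.2 days).
- Align Tables 14.2.12.1 and 14.2.12.5 with that text.
- In 6.1.7.11, define each stay as min(discharge, Day 28) minus max(admission, baseline), and state that the index admission counts. Set baseline to the time of first dose or, for a subject never dosed, to randomization. This is needed because the ITT population includes everyone randomized and Protocol 8.3 foresees randomized subjects who receive no study drug.
- Apply the same start rule to ICU stay in 6.1.7.10.
- Use one unit in the derivations and in the analyses.

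The cost is SAP wording and one standard procedure. The downside is that the U.S. covariate adjustment is no longer part of the main test.
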